6.3. Adjustments for Covariates

Unless otherwise specified, the statistical analysis models for the Treatment Period efficacy and health outcome analysis will include the stratification factor, baseline disease severity (IGA 3 versus 4). The stratification factor will not include age group, because the study will be conducted on adults (age 18 to 55 years) in the US.

In general, when an MMRM is to be used for analyses, treatment, baseline value, visit, the interaction of the baseline value-by-visit, the interaction of treatment-by-visit, and the stratification factor, baseline disease severity (IGA 3 versus 4), will be included as covariates; when an ANCOVA is to be used for analyses, baseline value will be included as a covariate.

6.4. Handling of Dropouts or Missing Data

Depending on the estimand being addressed, different methods will be used to handle missing data. The description of estimands can be found in Section [6.2](#).

[Table KGAK.6.4](#) describes the planned imputation methods for efficacy and health outcome endpoints for the treatment period.

Table KGAK.6.4. Imputation Techniques for Various Variables During Treatment Period

Type of Endpoints	Efficacy and Health Outcome Endpoints	Estimand of Secondary Endpoints (Analysis Strategy for Intercurrent Events)	Missing Data Imputation Method (Analysis Method)
Categorical	IGA, EASI, Pruritus NRS, Skin Pain NRS, and Sleep-loss related categorical endpoints at prespecified timepoints	Primary Estimand (Hybrid)	MCMC-MI (CMH)
		Supportive Estimand (Composite)	NRI (CMH)
	Remaining categorical endpoints	Supportive Estimand (Composite)	NRI (CMH)
Continuous	EASI percent change, Pruritus NRS percent change, Skin Pain NRS percent change, and Sleep-loss change from baseline	Primary Estimand (Hybrid)	MCMC-MI (ANCOVA)
		Supportive Estimand (Hypothetical)	No imputation (MMRM)
	Remaining continuous endpoints collected at multiple postbaseline timepoints including (but not limited to) BSA and POEM	Supportive Estimand (Hypothetical)	No imputation (MMRM)
	Remaining continuous endpoints collected only once postbaseline (if any)	Supportive Estimand (Hypothetical)	LOCF (ANCOVA)

Abbreviations: ANCOVA = analysis of covariance; BSA = body surface area; CMH = Cochran-Mantel-Haenszel; EASI = Eczema Area and Severity Index; IGA = Investigator's Global Assessment; LOCF = last observation carried forward; MCMC-MI = Markov chain Monte Carlo multiple imputation; MMRM = mixed-model repeated measures; NRI = nonresponder imputation; NRS = Numeric Rating Scale; POEM = Patient-Oriented Eczema Measure.

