
 To compare the seroresponses to the Tdap and MCV between lebrikizumab-treated and placebo-treated participants with moderate to severe AD 	
The percentage of participants who:
 
 1. Develop a booster response to tetanus toxoid 4 weeks after the administration of the Tdap vaccine (Week 16) Booster response is defined as: 
 ○ ≥ 4-fold increase in antitetanus IgG antibody concentration if the prevaccination level was >0.10 IU/mL and ≤ 2.7 IU/mL; OR ○ ≥ 2-fold increase in antitetanus IgG antibody concentration if the prevaccination level was >2.7 IU/mL; OR ○ ≥ 4-fold increase in antitetanus IgG antibody concentration and a postvaccination level ≥ 0.10 IU/mL if the prevaccination level was ≤ 0.10 IU/mL 2. Have positive antibody response to Meningococcus C antigen of the MCV 4 weeks after the administration of the vaccine (Week 16) Positive antibody response to Meningococcus C antigen of the MCV is defined as: 
 ○ postvaccination rSBA titer ≥ 4 times the LLOQ, if the prevaccination rSBA titer is less than the LLOQ; OR ○ postvaccination rSBA titer ≥ 4 times the prevaccination titer, if the prevaccination rSBA titer is greater than or equal to the LLOQ

Objectives	Endpoints
Secondary	

 To compare the efficacy of lebrikizumab with that of placebo in the treatment of patients with moderate-to-severe AD To compare the patient-reported outcomes between lebrikizumab-treated and placebo-treated participants with moderate-to-severe AD 	
Percentage of participants at Week 16
 
 with an IGA score of 0 or 1 and a reduction of ≥ 2 points from baseline achieving EASI 75 achieving EASI 90 achieving ≥ 4-point improvement from baseline in Pruritus NRS score who had baseline Pruritus NRS ≥ 4 
Percentage change from baseline to Week 16 in
 
 EASI Pruritus NRS 
Change from baseline to Week 16 in
 
 BSA Sleep-loss score

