6.2.2. Secondary and Supportive Estimands for Secondary Endpoints

The secondary estimand for secondary endpoints is a hybrid estimand representing the secondary clinical question of interest: what is the difference between treatment conditions (that is lebrikizumab vs placebo), in the target participant population, of successful response rates or means achieved after 16 weeks, without use of rescue medication, and if all participants continued with treatment except those who discontinued due to lack of efficacy?

The **secondary estimand for secondary endpoints** is described by the following attributes:

- Population: Defined through appropriate inclusion/exclusion (I/E) criteria to reflect the targeted patient population for approval
- Endpoint: Apply to all secondary endpoints
- How to account for ICEs:
 - Subjects who used rescue medication or discontinued treatment because of lack of efficacy prior to Week 16 will be considered as treatment failures, that is, nonresponder, after the ICEs. Therefore, composite strategy is used for these types of ICEs
 - For subjects who discontinued treatment because of reasons other than lack of efficacy prior to Week 16, a hypothetical strategy will be used to estimate what the treatment effect would have been if subjects continued with treatment. Therefore, hypothetical strategy is used for these types of ICEs
- Population-level summary: Difference in response proportions or means between treatment conditions

The **supportive estimand for categorical secondary endpoints** is a composite estimand as described by the following attributes:

- Population: Defined through appropriate I/E criteria to reflect the targeted patient population for approval
- Endpoint: Apply to all category secondary endpoints
- How to account for ICEs:
 - Subjects who used rescue medication or discontinued treatment prior to Week 16 will be considered as treatment failures, that is, nonresponder, after the ICEs. Therefore, composite strategy is used for these types of ICEs
- Population-level summary: Difference in response proportions between treatment conditions

The **supportive estimand for continuous secondary endpoints** is a hypothetical estimand as described by the following attributes:

- Population: Defined through appropriate I/E criteria to reflect the targeted patient population for approval
- Endpoint: Apply to all continuous secondary endpoints
- How to account for ICEs:

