 - For subjects who used rescue medication or discontinued treatment prior to Week 16, a hypothetical strategy will be used to estimate what the treatment effect would have been if rescue medications were not available and all subjects adhered to the treatment. Therefore, hypothetical strategy is used for these types of ICEs
- Population-level summary: Difference in means between treatment conditions

Table KGAK.6.3 summarized secondary and its supportive estimands.

Table KGAK.6.3. Description of Secondary and Supportive Estimands for Secondary Endpoints

Estimand	Analysis Strategy for Intercurrent Events			Missing Data Imputation Method	
	Rescue Medication	Treatment Discontinuation			
		Due to Lack of Efficacy	Due to Any Other Reasons		
Primary Estimand (Hybrid)	Composite: Set to baseline	Composite: Set to baseline	Hypothetical: Set to missing	Primary analysis: MCMC-MI	
Supportive Estimand for Categorical Endpoints (Composite)	Composite: Set to nonresponder	Composite: Set to nonresponder	Composite: Set to nonresponder	NRI	
Supportive Estimand for Continuous Endpoints (Hypothetical)	Hypothetical: Set to missing	Hypothetical: Set to missing	Hypothetical: Set to missing	MMRM, LOCF	

Abbreviations: AD = atopic dermatitis; LOCF = last observation carried forward; MCMC-MI = Markov chain Monte Carlo multiple imputation; MMRM = mixed-model repeated measures; NRI = nonresponder imputation; TCS = topical corticosteroids.

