6.4.2. Mixed-Model for Repeated Measures

Mixed-model for repeated measures analyses will be performed on continuous endpoints to mitigate the impact of missing data. This approach assumes missing observations are missing at random (missingness is related to observed data) and borrows information from participants in the same treatment arm taking into account both the missingness of data through the correlation of the repeated measurements.

The values subsequent to rescue medication use (high-potency TCS or systemic AD treatment, defined in [Appendix 2](#)) or treatment discontinuation will be made missing before applying the MMRM. The MMRM is described in Section [6.1.2](#).

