Measure	Variable	Analysis Method (Section 6.1)	Population (Section 6.1.1)	Comparison/Time Point	Analysis Type
	Proportion of participants achieving IGA (0)	CMH analysis with MCMC-MI	mITT	LEB 250 mg Q2W vs PBO; Week 16 and all scheduled visits in the Treatment Period	Secondary analysis
Eczema Area and Severity Index (EASI)	Change from baseline in EASI score	ANCOVA with MCMC-MI	mITT	LEB 250 mg Q2W vs PBO; Week 16 and all scheduled visits in the Treatment Period	Secondary analysis
	Percent change from baseline in EASI score		PPS	LEB 250 mgQ2W vs PBO; Week 16 and all scheduled visits in the Treatment Period	Supplementary analysis
			mITT	LEB 250 mg Q2W vs PBO; Week 16 and all scheduled visits in the Treatment Period	Supplementary analysis
	Proportion of participants achieving EASI 75	CMH analysis with MCMC-MI	mITT	LEB 250 mgQ2W vs PBO; Week 16 and all scheduled visits in the Treatment Period	Secondary analysis
	Proportion of participants achieving EASI 90		PPS	LEB 250 mg Q2W vs PBO; Week 16 and all scheduled visits in the Treatment Period	Supplementary analysis
			mITT	LEB 250 mg Q2W vs PBO; Week 16 and all scheduled visits in the Treatment Period	Supplementary analysis
	Proportion of participants achieving EASI 50	CMH analysis with MCMC-MI	mITT	LEB 250 mg Q2W vs PBO; Week 16 and all scheduled visits in the Treatment Period	Secondary analysis

Measure	Variable	Analysis Method (Section 6.1)	Population (Section 6.1.1)	Comparison/Time Point	Analysis Type
Body Surface Area (BSA) Affected by AD	Change from baseline in BSA score	MMRM	mITT	LEB 250 mg Q2W vs PBO; Week 16 and all scheduled visits in the Treatment Period	Secondary analysis
Pruritus Numeric Rating Scale (NRS)	Change from baseline in Pruritus NRS	ANCOVA with MCMC-MI	mITT	LEB 250 mg Q2W vs PBO; Week 16 and all scheduled visits in the Treatment Period	Secondary analysis
	Percent Change from baseline in Pruritus NRS	MMRM	mITT	LEB 250 mg Q2W vs PBO; Week 16 and all scheduled visits in the Treatment Period	Supplementary analysis
	Proportion of participants achieving at least 4-point improvement in pruritus NRS in participants who had baseline pruritus NRS ≥ 4	CMH analysis with MCMC-MI	mITT participants with baseline pruritus NRS ≥ 4	LEB 250 mg Q2W vs PBO; Week 16 and all scheduled visits in the Treatment Period	Secondary analysis
		CMH analysis with NRI	mITT participants with baseline pruritus NRS ≥ 4	LEB 250 mg Q2W vs PBO; Week 16 and all scheduled visits in the Treatment Period	Supplementary analysis

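### BSA is a secondary endpoint, but the SAP never estimates for it the hybrid estimand that Section 6.2.2 assigns to every secondary endpoint

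*SAP*

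**What the plan says.** - **Endpoint status.** BSA change from baseline is a secondary endpoint in protocol Section 3 and in SAP Table KGAK.4.1.
- **Estimand.** The hybrid estimand in SAP 6.2.2 has the scope "Apply to all secondary endpoints". Its summary measure is stated as "Population-level summary: Difference in response proportions or means between treatment conditions", so continuous endpoints are included. Table KGAK.6.3 implements it as "Composite: Set to baseline" after rescue or discontinuation for lack of efficacy, with MCMC-MI for the remaining missing data. (The text of 6.2.2 calls this estimand secondary and Tables KGAK.6.3 and KGAK.6.4 call it primary; the content is the same.)
- **Assignment of BSA.** Table KGAK.6.4 puts BSA in the row "Remaining continuous endpoints collected at multiple postbaseline timepoints including (but not limited to) BSA and POEM", whose only entry is the supportive hypothetical estimand with MMRM and no imputation.
- **Data handling.** Under SAP 6.4.2, values after rescue medication "or treatment discontinuation will be made missing before applying the MMRM".
- **Analysis list.** In Table KGAK.6.7 the variable "Change from baseline in BSA score" has one row: MMRM in the mITT population, typed as a secondary analysis.
- **Seeds.** Table KGAK.6.5 has seed pairs for IGA, EASI, Pruritus NRS, Skin Pain NRS and Sleep-loss, and none for BSA.

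**The concern.** The estimand section and the analysis tables disagree about which question the BSA result answers. A reader of 6.2.2 will take a rescued participant to count as a failure on BSA. The analysis that will be run estimates instead what would have happened had rescue not been available and everyone stayed on treatment. For BSA the supportive estimand stands alone, and the estimand it is meant to support is missing.

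No exemption or reason is given, and the pattern looks like an oversight. Skin Pain NRS, exploratory in both documents, receives the hybrid analysis and its own seeds, while BSA is grouped with exploratory POEM. The SAP Version 2 log says Section 6.4 was amended to match the estimand definitions. BSA and EASI are scheduled at the same visits in the protocol's Schedule of Activities, so the timing of collection does not explain different handling.

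What is at stake is interpretation. BSA and EASI would be reported together as secondary results while their lead analyses answer different questions.

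**Working it through.** The plan states no figure for this point, so the check is a comparison of the tables followed by an illustration on assumed values.

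**Step 1. Tables side by side (continuous endpoints).**

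| Endpoint | Status, Table KGAK.4.1 | Table KGAK.6.4 | Seeds, Table KGAK.6.5 |
|---|---|---|---|
| EASI percent change | Secondary | Hybrid (MCMC-MI, ANCOVA) and hypothetical (MMRM) | Yes |
| Pruritus NRS percent change | Secondary | Both | Yes |
| Sleep-loss change | Secondary | Both | Yes |
| BSA change | Secondary | Hypothetical (MMRM) only | No |
| Skin Pain NRS percent change | Exploratory | Both | Yes |
| POEM change | Exploratory | Hypothetical (MMRM) only | No |

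BSA is the only continuous endpoint listed as secondary in Table KGAK.4.1 that has no hybrid analysis. In Table KGAK.6.7 the MMRM for Pruritus NRS and Sleep-loss is supplementary, beside a secondary ANCOVA with MCMC-MI. For BSA the MMRM is the secondary analysis and nothing stands beside it.

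**Step 2. Where the two estimands part.** Discontinuation for reasons other than lack of efficacy is set to missing under both. They differ only after rescue (high-potency topical corticosteroid or systemic therapy, SAP Appendix 2) and after discontinuation for lack of efficacy.

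**Step 3. Illustration.** Assumed, not from the documents: mean BSA changes without rescue of -25 (lebrikizumab) and -12 (placebo) points; failure shares fL and fP; failure unrelated to outcome, so that the MMRM recovers the hypothetical means. A failure contributes a change of zero to the hybrid mean.

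- Hypothetical difference = -25 - (-12) = -13.0, whatever the failure shares.
- Hybrid difference = -25(1 - fL) + 12(1 - fP).
- Gap (hybrid minus hypothetical) = 25 fL - 12 fP.

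| fL / fP | Lebrikizumab mean | Placebo mean | Hybrid difference | Gap |
|---|---|---|---|---|
| 2% / 5% | -24.50 | -11.40 | -13.10 | -0.10 |
| 3% / 10% | -24.25 | -10.80 | -13.45 | -0.45 |
| 4% / 20% | -24.00 | -9.60 | -14.40 | -1.40 |
| 5% / 10% | -23.75 | -10.80 | -12.95 | +0.05 |
| 5% / 20% | -23.75 | -9.60 | -14.15 | -1.15 |
| 10% / 10% | -22.50 | -10.80 | -11.70 | +1.30 |
| 10% / 30% | -22.50 | -8.40 | -14.10 | -1.10 |

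The sign changes where 25 fL = 12 fP, that is fL/fP = 12/25 = 0.48. The largest gap shown is 1.40/13.0, about 11% of the difference; with rare failure it is 0.10/13.0, under 1%.

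**The case against.** The strongest reply is that the BSA analysis itself is not ambiguous. Table KGAK.6.4, Section 6.4.2 and Table KGAK.6.7 all specify the same MMRM, and Table KGAK.6.4 names the hypothetical estimand openly. A hypothetical-estimand MMRM is a legitimate choice. On this view only the scope line in 6.2.2 is too broad, and narrowing it removes the contradiction. The protocol's imputation text and seeds (Section 9.4.3.1) name IGA, EASI and Pruritus NRS, not BSA, and leave the details for continuous data to the SAP. The analysis-type label is also weak evidence, since Table KGAK.6.7 types POEM and Skin Pain NRS analyses as secondary too.

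Much of this stands: the MMRM is valid for its own estimand, and narrowing 6.2.2 is an acceptable minimum. It does not remove the inconsistency. The scope line has no exception, its summary measure covers means, and the plan as written leaves the estimand it states for BSA without an estimate.

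A second reply concerns timing. SAP Version 3 was approved after the Week 16 database lock, and Section 6.16 records that statisticians had patient-level data by then. Replacing the lead BSA analysis now would be a post-unblinding change. That also stands, and it shapes the fix. By the revision log, however, the estimand definitions entered in Version 2, approved before unblinding of that lock, so a hybrid BSA analysis would carry out a commitment already made.

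Two stronger readings are tempting. A reader might infer that removing post-rescue data flatters whichever arm is rescued more. The illustration does not support this: with equal 10% shares the MMRM difference exceeds the hybrid by 1.30 points in lebrikizumab's favour, and at 5% / 10% the less-rescued arm gains slightly more (1.25 against 1.20). A reader might also infer that BSA cannot be compared with EASI. Table KGAK.6.4 gives EASI percent change a supportive MMRM under the same hypothetical estimand, and BSA can be read beside that. Only the lead analyses fail to match.

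**Conclusion.** The inconsistency is real and should be corrected. The estimand that 6.2.2 states for all secondary endpoints is not estimated for BSA, and no passage exempts it.

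The numerical consequence is unknown in size and direction, because the documents give neither failure shares nor expected BSA changes. On the assumed changes and the shares tabulated, the hybrid difference lies between -11.7 and -14.4 against -13.0. That range rests on failure being unrelated to outcome and is an illustration, not a forecast.

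Importance is limited. Protocol Section 9.1 calls the study descriptive with no planned hypothesis testing, SAP 6.1.2 makes no multiplicity adjustment, and the co-primary vaccine-response analyses do not depend on this point.

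PROMIS Anxiety and Depression raise the same question: they are secondary in protocol Section 3, listed as exploratory in SAP Table KGAK.4.1, and analysed in Table KGAK.6.7 only by ANCOVA with LOCF.

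**What to change.** 1. Add BSA to the hybrid row of Table KGAK.6.4 and to Table KGAK.6.7: set to baseline after rescue or discontinuation for lack of efficacy, MCMC-MI for the rest, ANCOVA. Add a seed pair for BSA to Table KGAK.6.5.
2. Keep reporting the prespecified MMRM for BSA and label it as the hypothetical estimand.
3. Date the addition and state in the SAP and the clinical study report that it was made after the Week 16 lock.
4. Settle the status of the PROMIS scores and reconcile 6.2.2 with their LOCF-only analysis.

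At minimum, limit the scope line in 6.2.2 to the endpoints that Table KGAK.6.4 assigns to the hybrid estimand, and state that BSA targets the hypothetical estimand only.

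The cost is a few table edits, one more run of existing imputation and ANCOVA code, and the disclosure. The minimum option costs one or two sentences. No new data are needed.

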6.4.1. Markov Chain Monte Carlo Multiple Imputation

The method of handling missing efficacy data as mentioned in [Table KGAK.6.4](#) will be as follows for both binary and continuous endpoints.

For participants who receive rescue medication (high-potency topical corticosteroids [TCS] or systemic AD treatment, defined in [Appendix 2](#)) or discontinue from the study treatment due to lack of efficacy, values should be set to the participant's baseline value subsequent to this time through Week 16. The Markov chain Monte Carlo multiple imputation (MCMC-MI) will be used to handle the remaining missing data. Imputation will be conducted within each treatment group independently so the pattern of missing observations in 1 treatment group cannot influence

missing value imputation in another. The SAS PROC MI with the MCMC option will be used to conduct the MCMC-MI. The imputation model will include the relevant baseline and postbaseline.

For each imputation process, 25 datasets with imputations will be calculated. The initial seed values are given in [Table KGAK.6.5](#). Each complete data set will be analyzed with the specified analysis. The results from these analyses will be combined into a single inference using SAS PROC MIANALYZE.

For binary responses related to the Eczema Area and Severity Index (EASI) and IGA, the binary response variables will be calculated based on the multiply imputed datasets that have been created. Because the MCMC algorithm is based on the multivariate normal model, imputed values for IGA will not generally be one of the discrete values used in IGA scoring (0, 1, 2, 3, or 4). Therefore, to derive the binary IGA response variable, standard rounding rules will be applied to the imputed values. For example, if a participant has an IGA score imputed as 1.4 (and assuming a baseline IGA score of 3), the imputed value would be rounded down to 1, and the minimum change from baseline of 2 would have been met. This participant would be considered a responder.

For derivation of a $\geq 75\%$ reduction from baseline in EASI score (EASI 75) and $\geq 90\%$ reduction from baseline in EASI score (EASI 90) response, no rounding will be performed. The imputed Week 16 EASI value will be compared directly to the observed baseline EASI value to determine whether a reduction of at least 75% or 90% was achieved.

The approach of handling missing data for Pruritus NRS, Skin Pain NRS, and Sleep-loss are the same. Using Pruritus NRS as an example, for derivation of the following Pruritus NRS responses, no rounding will be performed. The imputed Pruritus NRS value will be compared directly to the observed mean baseline Pruritus-NRS value to determine whether a response was achieved:

- Percentage of participants with a Pruritus NRS of ≥ 4 -points at baseline who achieve a ≥ 4 -point reduction from baseline at Week 16

Imputation of continuous data will parallel that of binary variables. The imputed values will be used for the secondary endpoints, such as

- Percentage change in Pruritus NRS from baseline
- Percentage change in EASI score from baseline
- Percentage change in Skin Pain NRS from baseline.

Table KGAK.6.5. Seed Values for MCMC-MI

Analysis	Seed values	
	Lebrikizumab 250 mg Q2W	Placebo
IGA and its related derived endpoints	970309630	1477266806
EASI and its related derived endpoints	353985587	1828572477
Pruritus NRS and its related derived endpoints	1611917356	1087836192
Skin Pain NRS and its related derived endpoints	345235233	352342343
Sleep-loss score and its related derived endpoints	574563534	645745224

Abbreviations: EASI = Eczema Area and Severity Index score; IGA = Investigator's Global Assessment; MCMC-MI = Markov chain Monte Carlo multiple imputation; NRS = Numeric Rating Scale; Q2W = every 2 weeks.

